of a PWM program; and 3) Evaluation of “readiness to change” and “barriers to making lifestyle changes” with motivational interviewing during the orientation session, allowing for interventions tailored to the patient’s needs. The proposed study is a pilot pragmatic trial designed to test the feasibility, acceptance, and preliminary effectiveness of the BPE (*Intervention* group: N=40) vs. standard-of-care (*Control* group: N=20) for adolescents with severe obesity in PWM programs at two POWER sites. The primary aims are: 1) Test whether existing PWM programs can successfully implement the BPE for 80% of participants randomly assigned to the *Intervention* group and 2) Test whether 70% of participants in the *Intervention* group will complete 26 contact hours during 6 months of treatment. The secondary aims test whether the *Intervention* group has greater rates of participation and retention, plus better health outcomes compared to the *Control* group. If the results of this pilot study are promising, then a fully-powered multi-site clinical trial can be designed to evaluate the BPE’s efficacy in existing PWM programs. By developing more successful evidence-based interventions for PWM programs, this research can help reverse the adolescent obesity epidemic and prevent the onset or worsening of comorbidities.

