Primary Aim 1 (Feasibility): Test whether existing multi-component PWM programs can successfully implement the BPE for adolescents with severe obesity using existing clinical staff. Successful implementation of the BPE will be defined as ≥80% of the *Intervention* group participants randomly assigned to the *Intervention* group and their parent/guardian attending the individual program orientation *prior to* the initial medical assessment visit of the PWM program. The program orientation will include: 1) Validated mental health questionnaires to assess cognitive, emotional and behavioral problems, anxiety, and binge eating disorder; 2) Clinical evaluation of “readiness to change” and barriers to lifestyle changes, using motivational interviewing; and 3) Scheduling of follow-up interactive encounters (FIEs: telehealth visits, phone calls, and/or email exchange) for the 1st month of the 6-month treatment period. For the remaining 5 months of treatment, participants in the *Intervention* group will be scheduled monthly for FIEs between clinic visits to achieve a total of 26 contact hours when combined with standard-of-care clinic visits and group sessions, if offered.

Hypothesis 1.1: 80% of participants in the *Intervention* group (N=40) will successfully complete all components of the BPE in the program orientation session (as described above), with existing clinical staff in their respective multi-component PWM program.

Hypothesis 1.2: 80% of participants in the *Intervention* group will successfully schedule FIEs between clinic visits for the remaining 5 months of the 6-month treatment period to achieve a total of 26 contact hours.

Primary Aim 2 (Acceptability): Evaluate rates of retention and attrition among participants in the *Intervention* group

Hypothesis 2.1: 70% of participants in the *Intervention* group will complete 26 contact hours (including standard-of-care clinic visits, group sessions, and FIEs between clinic visits) during the 6-month treatment period.

Hypothesis 2.2: 70% of the scheduled FIEs will be completed by participants in the *Intervention* group.

Secondary Aim 3 Test whether the *Intervention* group has greater rates of participation and retention in standard-of-care clinic visits and group sessions (if offered) compared to the *Control* group.

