Program Orientation – Immediately after the screening visit, participants assigned to the *Intervention* group will attend an individual Program Orientation session. This will include the following: 1) Detailed site-specific description of the PWM program; 2) Assessment of “readiness to change” and barriers to lifestyle changes using motivational interviewing strategies, including “confidence rulers”; 3) Completion of selected validated mental health assessment questionnaires; and 4) Scheduling of FIEs between clinic visits. The frequency, time spent, and type of FIE will take into consideration the needs of each patient-family enrolled in the study. The adolescent and parent/guardian will determine whether they will participate together during a FIE, do them separately or have a combination of the two. The frequency of contact between clinic visits will be determined by the number of contact hours provided by clinic visits as part of the “standard-of-care” over a 6-month treatment. The goal for the *Intervention* group is to have a total of 26 provider contact hours over the 6-month treatment period. After accounting for the contact hours from clinic visits as part of the “standard of care”, the balance of the 26 contact hours will consist of FIEs scheduled between clinic visits. At the end of the Program Orientation, the subject and parent/guardian will schedule FIEs and use tracking calendar booklet provided to keep record of their scheduled clinic visits and FIEs for the first month of treatment. A summary of the findings from the mental health assessment measures, assessment of “readiness to change” and barriers to lifestyle change for each subject in the *Intervention* group will be reviewed with the clinical team at each site prior to the initial medical visit with PWM program (Table 1). **Baseline Assessment** - Each participant (*Intervention and Control groups*) will complete at their initial medical visit with the PWM program a baseline assessment that includes the following measures: 1) Anthropometric measurements (height and weight); 2) Body composition assessment (% body fat, skeletal muscle mass, fat-free mass); and 3) Blood pressure (systolic and diastolic). Fasting blood work (plasma lipids, glucose, liver enzymes, and hemoglobinA1c) will be obtained up to 3 months prior to the initial medical visit or up to 6 weeks after the initial medical assessment visit. Fasting blood samples will be drawn for the laboratory analyses by qualified staff at a certified medical laboratory affiliated with CCHMC and HDVCH. Standardized methods and analytic procedures will be done for each blood parameter. The results of all clinical measurements and laboratory values, and referrals and/or additional clinic visits made to address mental health concerns will be recorded on the study’s source document, specific for each subject. In addition contact time and provider types involved in the initial medical visit will also be recorded (Table 1).

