2	% of scheduled FIEs between clinic visits completed (Intervention Group only)	
	% of subjects that achieve 26 hours of contact time (Intervention Group only)	
3	% of scheduled standard-of-care clinic visits attended (Intervention and Control Groups)	Clinical Assessment Visits (Intervention and Control Groups) Baseline, 3-, and 6-month assessments Tracking form for anthropometric and body composition measurements, and blood pressure.
	% of subjects that complete 6-month treatment period (Intervention and Control Groups)	
4	Anthropometric measurements (height, weight) BMI outcome metric: % of the 95 th percentile for BMI	
	Body composition (% body fat, skeletal muscle mass, fat-free mass)	
	Blood pressure (systolic, diastolic)	
4	Laboratory values* (fasting) (HbA1c, ALT, glucose, non-HDL cholesterol, and TG)	Clinical Assessment Visits (Intervention and Control Groups) Baseline and 6-month assessments Tracking form for laboratory measures

Three-month and Six-month Assessments: Participants will be assessed following the same procedures as for the baseline assessment, with measurement of height, weight, body composition, and blood pressure. If the participant is at Tanner stage I, II, or III at the baseline visit, Tanner staging will be assessed again at the six-month visit. Fasting blood work will be obtained at the 6-month assessment visits. The results of all clinical measurements and laboratory values will be recorded on the study's source document, specific for each subject (Table 1). Completion of the 3-month and 6-month reassessment clinic visits can occur 2-weeks prior or 4 weeks after the 3-month and 6-month time points.

Table 1 Schedule of Procedures

Elapsed Time	Screening Visit	Baseline Medical Visit	#Month 3 Medical Assessment	#Month 6 Medical Assessment	Telehealth/Phone/Email remote encounters between visits	Other clinical in-person encounters
Randomization	X					
Height and Weight	X	X	X	X		X
Body Composition (%body fat, skeletal muscle mass, fat-free mass)		X	X	X		X
Blood Pressure		X	X	X		X
Demographics	X					
Program orientation session detailing site-specific description of pediatric weight management program	X*					
Mental Health Assessments	X*					
Readiness to change assessment	X*					
Schedule Follow-up Interactive Encounters		X*	X*		X*	X*
Review Medical History		X	X	X		X
Physical Exam		X	X	X		X
Blood for serum chemistry		X		X		
Assess for adverse events		X	X	X	X	X
Medication Review		X	X	X		X

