8. DATA ANALYSIS

8.1. Study Endpoints

Demographic and clinical characteristics will be summarized overall and within each center using frequency and percent for categorical data and median and interquartile range for the continuous measurements. For each aim below, the two-sided 95% confidence intervals will be calculated using the Score Confidence Interval.³⁴ All comparisons between the intervention and control groups will be tested at the two-sided, 5% level of significance.

Aim 1: For patients in the intervention group only, percentages and two-sided 95% confidence intervals will be presented for the each of the components of the “Bundle of Program enhancements (BPE)”: a) percent of participants attending the program orientation; b) percent of participants completing each of the mental health questionnaires; 3) percent of participants completing the “readiness to change” clinical assessment; 4) percentage of participants that complete scheduling of interactive encounters (FIE) between clinic visits for 1st month of treatment; and 5) Percent of participants that complete scheduling of FIE between clinical visits for each of months 2-6 of treatment. Each confidence interval will be examined to determine if the hypothesized value of 80% is contained within the interval.

Aim 2: For patients in the intervention group only, the percentages and two-sided 95% confidence intervals will be calculated for the intervention group only for the percent of patients that complete at least 26 contact hours during the 6-month treatment period. The confidence interval will be examined to determine if the hypothesized value of 70% is contained within the interval. In addition, the mean and 95% confidence interval will be presented for the percent of FIE completed by each patient and also for the total number of contact hours completed by each patient. These measures will also be provided for the subset of patients in the intervention group that are identified with mental health problems and descriptively compared to the subset of patients in the intervention group without mental health problems.

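### Section 8.1 gives no estimate of the share of Intervention participants who complete all orientation components (Hypothesis 1.1), and no single participant-level proportion scheduled to 26 contact hours (Hypothesis 1.2)

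*Combined protocol and SAP*

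**What the plan says.** The combined protocol and SAP states the Aim 1 target in several ways.

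- **Section 1, Abstract:** the aim is to "Test whether existing PWM programs can successfully implement the BPE for 80% of participants" in the Intervention group.
- **Section 3, Primary Aim 1:** "Successful implementation of the BPE will be defined as ≥80"% of Intervention participants, with a parent or guardian, attending orientation before the initial medical visit.
- **Section 3, Hypothesis 1.1:** 80% of the Intervention group (N=40) "will successfully complete all components of the BPE in the program orientation session". The content listed there is the questionnaires ("Validated mental health questionnaires to assess cognitive, emotional and behavioral problems, anxiety, and binge eating disorder"), a clinical evaluation of readiness to change and of barriers, and scheduling of the first month's follow-up interactive encounters (FIEs).
- **Section 3, Hypothesis 1.2:** 80% will schedule FIEs "for the remaining 5 months of the 6-month treatment period to achieve a total of 26 contact hours".
- **Section 6, Table 1 (Key Outcome Measures):** the orientation components appear as separate rows. The 26-hour scheduling outcome has its own Aim 1 row. There is no all-components row.
- **Section 8.1, Aim 1:** "percentages and two-sided 95% confidence intervals will be presented for the each of the components", namely attendance, each questionnaire, readiness to change, month-1 scheduling, and scheduling in each of months 2 to 6. Each interval is checked for whether it contains 80%. In Section 8.1 the 26-hour threshold appears only under Aim 2, for hours completed, against 70%.

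**The concern.** Hypothesis 1.1 describes one yes/no result per participant: everything in orientation was done, or it was not. Section 8.1 estimates the separate rates. A report that followed it exactly would omit the quantity that Hypothesis 1.1 sets against 80%. It could also show every component as compatible with 80% when the all-components rate is not.

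Hypothesis 1.2 raises a milder form of the same problem. Its outcome is named in Table 1, but the analysis section turns it into five monthly rates without a stated hours criterion.

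Feasibility rates are the main product of this pilot, and Section 3 makes the design of a larger trial depend on them. If the joint endpoint is built only after the data are seen, the choice of items and denominator is open to the result.

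**Working it through.** **Inputs from the documents.** n = 40 in the Intervention group (Section 8.2); two-sided 95% score interval and an 80% reference (Section 8.1); orientation content (Sections 3 and 6).

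**Assumed inputs.** The documents give no component rates. I take 36 of 40 attending and five further items: three questionnaires (one for each problem area named in Section 3), the readiness and barriers evaluation counted as one item, and month-1 scheduling. Section 6 places all of these in orientation (on scheduling: "At the end of the Program Orientation, the subject and parent/guardian will schedule FIEs"), so a non-attender misses all five.

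**1. Reproduce Table 2 of Section 8.2.** Score interval with z = 1.96 and p = x/n:

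[p + z²/2n ± z√(p(1−p)/n + z²/4n²)] / (1 + z²/n)

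| x/40 | Computed | Table 2 |
|---|---|---|
| 20 (50%) | 35.2–64.8% | 35–65% |
| 26 (65%) | 49.5–77.9% | 49–78% |
| 32 (80%) | 65.2–89.5% | 65–89% |
| 38 (95%) | 83.5–98.6% | 83–99% |

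Agreement is to within about half a percentage point. Table 2 is not in dispute.

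**2. Counts whose interval contains 80%.** 27/40 gives 52.0–79.9% (excluded); 28/40 gives 54.6–81.9%; 36/40 gives 76.9–96.0%; 37/40 gives 80.1–97.4% (excluded). So the interval contains 80% for 28 to 36 completers.

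**3. Range of the joint count.** If each of the five items is completed by x of the 36 attenders, there are 5(36 − x) misses. The joint count is largest, x, when all misses fall on the same people. It is smallest, 36 − 5(36 − x), when they fall on different people.

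| x per item | Component interval | Joint count, low to high |
|---|---|---|
| 36 | 76.9–96.0% | 36 to 36 |
| 34 | 70.9–92.9% | 36 − 10 = 26 to 34 |
| 32 | 65.2–89.5% | 36 − 20 = 16 to 32 |

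The same component rates fit very different joint rates, which is why the joint rate cannot be recovered from them. In the last row every component interval contains 80%. The joint interval excludes 80% once the 20 misses fall on 9 or more attenders (36 − 9 = 27).

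**4. Expected joint rate with clustering.** The low ends are bounds, not expectations. Use a beta-binomial among attenders with p = x/36 and correlation ρ. With s = (1 − ρ)/ρ, the chance that an attender completes all five is the product over i = 0 to 4 of (ps + i)/(s + i). Multiply by 36/40.

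| x | ρ = 0.2 | ρ = 0.5 | ρ = 0.8 |
|---|---|---|---|
| 34 | 73.6% (29.5/40) | 79.1% (31.6/40) | 82.9% (33.2/40) |
| 32 | 59.7% (23.9/40) | 69.2% (27.7/40) | 76.1% (30.4/40) |

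All three values for x = 34 lie within 28 to 36. For x = 32, the first is clearly below 28, the second is at the boundary and the third is inside.

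**5. Hypothesis 1.2, by comparison of text.** Table 1 asks whether a participant's scheduling reaches a 26-hour total. Section 8.1 item 5 gives a rate for each of months 2 to 6 and does not define complete scheduling. Section 6 says that FIEs make up the balance of the 26 hours and are scheduled monthly towards that target. Item 5 may therefore mean booking each month's share. Even so, five monthly rates are not one proportion of participants scheduled to 26 hours.

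**The case against.** **Success is defined as attendance, and Section 8.1 reports it.** This is true for participants, so a reader should not infer that Aim 1 has no analysed success criterion. It does not remove Hypothesis 1.1, which has its own wording and its own 80%.

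**The illustration seldom changes the conclusion.** This largely stands. Orientation is a single individual session, so misses should cluster. With full completion by attenders the gap is nil, and at 34/40 per item it is usually harmless. A reader might infer from the bounds of 26/40 and 16/40 that the planned analysis would generally mislead. The documents give no component rates, so they do not support that.

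**The Hypothesis 1.2 outcome is already in the plan.** This stands: it is a Table 1 outcome, and Section 6 supports reading item 5 as each month's share of the balance. A reader might also infer from the 3 [3, 7] visits by 6 months in the preliminary data that scheduled hours would fall far short of 26. Those are registry visits that took place, not planned hours, and they cannot show this.

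**Month-1 scheduling may not belong to orientation.** In the extracted Schedule of Procedures, the row "Schedule Follow-up Interactive Encounters" is marked at baseline and not at screening. Column positions in extracted text are unreliable, and Sections 3 and 6 both place it in orientation. I put no weight on that row.

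**It is a pilot without confirmatory testing, and the data are tracked anyway.** Both are true. They make the remedy cheap, and it asks only for estimates with intervals.

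**Conclusion.** The point holds and should be fixed. Hypothesis 1.1 has no matching estimate in Section 8.1 and no row in Table 1 (high confidence, from the text alone). For Hypothesis 1.2 the gap is narrower: the outcome is named, but Section 8.1 gives no single participant-level proportion. That gap is small if item 5 means each month's share of the 26-hour balance (moderate confidence).

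The numerical effect rests wholly on the assumed rates, five nested items and the assumed correlations. It runs from nothing, when attenders complete everything, to a changed conclusion at 32/40 per item when misses cluster only weakly to moderately. The attendance criterion in Section 3 is not challenged.

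**What to change.** In Section 8.1, Aim 1, add two yes/no endpoints per participant, each out of the 40 randomized to Intervention, with a score interval against 80%:

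- **(a) Hypothesis 1.1:** attended orientation and completed every mental health questionnaire, the evaluation of readiness to change and of barriers, and month-1 FIE scheduling. Add a matching row to Table 1 (Key Outcome Measures).
- **(b) Hypothesis 1.2, the existing Table 1 outcome:** scheduled FIE hours plus planned standard-of-care clinic and group hours total at least 26 over the 6 months.

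Keep the component and monthly rates as descriptive support, and state what counts as complete scheduling in item 5. Report the Section 3 attendance criterion separately, including the parent or guardian's attendance and its timing before the initial medical visit.

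**Cost:** a few sentences, one table row and two derived variables. Design, sample size and Table 2 are unchanged. The Table 1 tracking forms already cover attendance, assessments and scheduled FIEs. Confirm early that planned duration is stored for each scheduled FIE: Section 6 names FIEs scheduled, FIEs completed and time spent, but not planned duration. The downside is that the headline feasibility rate may be lower than the component rates.

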Six-month Treatment Period: *Intervention group* – Subjects will be scheduled for clinic visits and program group sessions (if offered) in accordance with the “standard of care” for the PWM program at each clinic location. Scheduling of remote FIEs (telehealth, phone call and/or email exchange) between clinic visits will be done on a monthly basis for the duration of the 6-month treatment period. The projected contact hours accumulated for the scheduled interactive encounters between clinic visits, when combined with the planned clinic visits and group sessions (if offered) is targeted to achieve 26 contact hours for the 6-month treatment period. These scheduled FIEs will be entered in the Twilio text messaging platform, which will automatically provide text message reminders of the scheduled FIEs. Twilio is also integrated with REDCap, which can provide reports on the FIEs scheduled, completed FIEs and time spent, provider type at encounter, and who participated (adolescent alone, parent/guardian alone and/or adolescent and parent/guardian together). *Control group* - Subjects will only receive the “standard of care” for weight management at their clinic location. Treatment data collection - Each clinic visit and group session attended, type of interactive encounter completed between clinic visits, and time spent by provider type, will be recorded on the study’s source document, specific to each subject. In addition referrals made and additional clinic visits completed to address mental health concerns, as indicated, will be recorded as well (Table 1).

Table 1. Key Outcome Measures for Primary Aims (in bold font) and Secondary Aims

Aim	Variable	Source
1	% of subjects attending program orientation	Program Orientation Session (Intervention Group only) Tracking form for attendance and completion of assessment measures, and documentation of scheduled FIEs
	% of subjects completing mental health assessment questionnaires	
	% of subjects completing "readiness to change" clinical assessment	
	% of subjects that complete scheduling of follow-up interactive encounters (FIEs) between clinic visits for 1 st month of treatment	
1	% of subjects that complete scheduling of FIEs between clinic visits to achieve a total of 26 contact hours when combined with standard-of-care clinic visit over the 6-month treatment period	6-month Treatment Period Tracking form for completion of clinic visits and FIEs between clinic visits, time spent, and provider type.

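### Does measuring FIE completion against scheduled FIEs (Hypothesis 2.2) overstate how much of the planned remote contact families accepted?

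*Combined protocol and SAP*

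**What the plan says.** Section 3, Hypothesis 2.2 states that "70% of the scheduled FIEs will be completed by participants" in the Intervention group. The key outcome table in Section 6 uses the same denominator: the percentage "of scheduled FIEs between clinic visits completed". Section 8.1, Aim 2 summarises it as a per-patient average: "the mean and 95% confidence interval will be presented for the percent of FIE completed by each patient".

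The denominator builds up over time. Month 1 is booked at the orientation session, and for the treatment period Section 6 says "Scheduling of remote FIEs (telehealth, phone call and/or email exchange) between clinic visits will be done on a monthly basis". The intended amount of FIE contact is what remains of 26 hours after standard-of-care time: "the balance of the 26 contact hours will consist of FIEs scheduled between clinic visits". How often it happens also depends on standard-of-care time: "The frequency of contact between clinic visits will be determined by the number of contact hours provided by clinic visits". Section 6 also lets frequency, duration and type of FIE vary with each family's needs.

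Three companion measures stand in Section 8.1:

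- Aim 1 gives the percentage of Intervention participants whose FIEs are scheduled, for month 1 and for each later month.
- Aim 2 gives the "percent of patients that complete at least 26 contact hours during the 6-month treatment period", with its interval compared with 70%.
- Aim 2 also gives the mean and interval for total contact hours.

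No text says how to treat a participant with no scheduled FIE, or whether a rebooked FIE counts once or twice.

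**The concern.** A completed-over-scheduled ratio rewards early disengagement. A family that books one month, attends well and then disappears contributes a good percentage, and the five empty months leave no trace in it. A family that never books is 0/0 and leaves the average. If disengagement shows up as not booking rather than as missed appointments, Hypothesis 2.2 describes the families and months in which contact was still wanted.

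Hypothesis 2.2 is one of two acceptability hypotheses in a pilot meant to inform a full trial. A reader who took 70% as the share of the planned remote contact that families accepted could be too optimistic. The same percentage also feeds the comparison of participants with and without mental health problems, where different rates of stopping would distort the contrast.

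**Working it through.** **Plan's own figures.** The documents compute nothing for Hypothesis 2.2. The related figures are the score intervals in Section 8.2, Table 2. The two-sided 95% score interval for 80% with N=40 is 65.2% to 89.5% (table: 65% to 89%). All eight intervals in the table reproduce within one point.

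**Inputs.** From the documents: 40 Intervention participants, six months, the 70% mark, and the 80% scheduling mark in Hypothesis 1.2, which leaves room for 8 of 40 not to complete scheduling. Assumed: equal planned FIEs each month; a share d stops booking after month m; e is their completion until then; c is completion in the others.

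**Families that stop booking.**

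- Reported mean: S = d·e + (1−d)·c
- Share of planned FIEs completed: P = d·e·m/6 + (1−d)·c
- Overstatement: S − P = d·e·(6−m)/6

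With d = 20% and S fixed at 70%, c = (0.70 − 0.2e)/0.8, and P is:

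| e | c | m=1 | m=2 | m=3 |
|---|---|---|---|---|
| 0.5 | 0.750 | 61.7% | 63.3% | 65.0% |
| 0.6 | 0.725 | 60.0% | 62.0% | 64.0% |
| 0.7 | 0.700 | 58.3% | 60.7% | 63.0% |
| 0.8 | 0.675 | 56.7% | 59.3% | 62.0% |

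The gap is 5 to 13 points. With d = 10% it is 2.5 to 7 points, with d = 5% it is 1 to 3, and with d = 0 it is zero.

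**Families that never book.** If k of 40 never book and the rest average 70%, the figure over all 40 is 70% × (40−k)/40: 68.25%, 66.5% and 63.0% for k = 1, 2 and 4. Few such families are likely, because month 1 is booked at an orientation held straight after the screening visit.

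**Rebooking.** Let each FIE booking be completed with probability p = 0.7, let a share r of missed FIEs be rebooked once, and let every booking count. The reported ratio stays at 70%, while the share of planned FIEs completed is p + r·p·(1−p): 75.25%, 80.5% and 91.0% for r = 0.25, 0.5 and 1. With d = 20% and e = c = 0.7, the two effects cancel when (0.2·m/6 + 0.8)(0.7 + 0.21r) = 0.70, that is r = 0.67, 0.51 and 0.37 for m = 1, 2 and 3. The sign therefore depends on rates that are not known.

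**What the companion measures would show when d = 20%.**

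- Monthly scheduling falls to 80% after month m.
- Suppose the stoppers would otherwise have gone on at rate e. Mean total contact hours then fall by d·e·(6−m)/6 times the planned FIE hours. That is the overstatement itself, expressed in hours.
- If 26 hours requires every planned FIE, at most 32·c participants, rounded down, can reach it: 24, 23, 22 or 21 of 40 (60%, 57.5%, 55%, 52.5%) for e = 0.5 to 0.8. Upper score limits are 73.7%, 71.5%, 69.3% and 67.1%.

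**The case for a change.** The best argument for a change is that the three marks can all look satisfied together. With d = 20% and e = 0.5 or 0.6, scheduling stands at its 80% mark and FIE completion at 70%. At the ceiling of 24 or 23 of 40, the 26-hour interval still contains 70%. Meanwhile only 60-65% of planned FIEs were completed. The schedule of procedures also ties FIE booking to visits and encounters, so a family that stops coming has no obvious occasion at which FIEs it will miss would be booked and counted.

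The first part stands as arithmetic, but it is a limit of the interval-contains-target rule with 40 participants, not of the FIE denominator. The 26-hour estimate would be 60% at best, and mean contact hours would be low; both are reported. The second part stands only in part. Sections 3 and 6 describe monthly scheduling for the whole six months, which would keep no-shows in the denominator. Neither says what happens with families that have disengaged, and the 80% mark accepts some failure.

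The obvious remedy is to divide completed FIE hours by a planned-hours figure for each site. It has costs of its own:

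- It ignores the tailoring of FIEs to each family and marks down a participant who reaches 26 hours through extra clinic time.
- It moves from counts to hours and largely repeats total contact hours.
- It needs standard-of-care hours that the documents do not give.

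**Conclusion.** No change is needed. Hypothesis 2.2 is conditional on scheduling and says so in both places where it is defined. Section 8.1 applies the 70% check only to the 26-hour percentage; the FIE percentage is an additional descriptive mean, the mental-health contrast is descriptive too, and Section 8.2 rules out confirmatory testing. The plan divides the question sensibly: scheduling under Aim 1, completion given scheduling under Hypothesis 2.2, and delivered contact through the 26-hour percentage and total hours. Aim 2 can be judged soundly from these together.

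The possible distortion runs from zero to about 13 points of overstatement when up to 20% of families stop booking, and up to 21 points of understatement (91% against 70%) when every missed FIE is rebooked and counted twice. All of this rests on assumed rates and equal months, so neither size nor direction is established. What is truly absent is a rule for participants with nothing scheduled and for rebooked FIEs. Section 6 describes a tracking system "which can provide reports on the FIEs scheduled, completed FIEs and time spent", so an analyst can state how many participants have no value and how rebookings were counted when the result is reported.
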